12.2 COMMON TERMINOLOGY CRITERIA FOR ADVERSE EVENTS V4.0 (CTCAE)

The descriptions and grading scales found in the revised NCI Common Terminology Criteria for Adverse Events (CTCAE) version 4.0 will be utilized for adverse event reporting. (<http://ctep.cancer.gov/reporting/ctc.html>)

12.3 RESPONSE EVALUATION OF HODGKIN AND NON-HODGKIN LYMPHOMA.

Response Evaluation of Hodgkin and non-Hodgkin lymphoma will occur via the 2007 International Working Group criteria (Cheson et al.); MDS response evaluation by International Working Group (IWG) criteria (Cheson et al.); AML evaluation via an international expert panel, on behalf of the European LeukemiaNet (Dohner et al.) (43-45).

12.3.1 CRITERIA FOR LYMPHOMA DISEASE ASSESSMENT

Table 2. Response Definitions for Clinical Trials

Response	Definition	Nodal Masses	Spleen, Liver	Bone Marrow
CR	Disappearance of all evidence of disease	(a) FDG-avid or PET positive prior to therapy; mass of any size permitted if PET negative (b) Variably FDG-avid or PET negative; regression to normal size on CT	Not palpable, nodules disappeared	Infiltrate cleared on repeat biopsy; if indeterminate by morphology, immunohistochemistry should be negative
PR	Regression of measurable disease and no new sites	≥ 50% decrease in SPD of up to 6 largest dominant masses; no increase in size of other nodes (a) FDG-avid or PET positive prior to therapy; one or more PET positive at previously involved site (b) Variably FDG-avid or PET negative; regression on CT	≥ 50% decrease in SPD of nodules (for single nodule in greatest transverse diameter!); no increase in size of liver or spleen	Irrelevant if positive prior to therapy; cell type should be specified
SD	Failure to attain CR/PR or PD	(a) FDG-avid or PET positive prior to therapy; PET positive at prior sites of disease and no new sites on CT or PET (b) Variably FDG-avid or PET negative; no change in size of previous lesions on CT		
Relapsed disease or PD	Any new lesion or increase by ≥ 50% of previously involved sites from nadir	Appearance of a new lesion(s) > 1.5 cm in any axis, ≥ 50% increase in SPD of more than one node, or ≥ 50% increase in longest diameter of a previously identified node > 1 cm in short axis Lesions PET positive if FDG-avid lymphoma or PET positive prior to therapy	> 50% increase from nadir in the SPD of any previous lesions	New or recurrent involvement

Abbreviations: CR, complete remission; FDG, [¹⁸F]fluorodeoxyglucose; PET, positron emission tomography; CT, computed tomography; PR, partial remission; SPD, sum of the product of the diameters; SD, stable disease; PD, progressive disease.

12.4 INTERNATIONAL PROGNOSTIC SCORING SYSTEM (IPSS) FOR MDS PROGNOSTIC VARIABLE

Survival and MDS Evolution Score Value

	0	0.5	1	1.5	2	
Marrow Blasts (%)	<5		5 to 10	N/a	11 to 20	21 to 30
Karyotype	Good Normal or any 1 of: - Y (del(5q) del(20q)		Intermed. Any other abnormality	Poor chromosome 7 anomalies; Complex: ≥ 3 abnormalities	n/a	n/a
Cytopenias Neutrophil Count < 1800/mcL Platelets < 100,000 mcL Hemoglobin < 10 g/dL	0 or 1		2 or 3	n/a	n/a	n/a
Low: total score = 0						
Int-1: total score 0.5-1.0						
Int-2: total score 1.5-2.0						
High: total score ≥ 2.5						

12.5 MDS RESPONSE CRITERIA:

Modified International MDS Working Group (IWG) Criteria for Measurement of Response/Treatment Effect in MDS will be used to assess response.

12.5.1 COMPLETE REMISSION (CR)

Bone marrow evaluation: Bone marrow showing < 5% myeloblasts with normal maturation of all cell lines, with no evidence for dysplasia (see dysplasia qualifier under peripheral blood evaluation). When erythroid precursors constitute < 50% of bone marrow nucleated cells, the percent of blasts is based on all nucleated cells; when there are \geq 50% erythroid cells, the percent blasts should be based on the non-erythroid cells.

- Peripheral Blood Counts (Absolute values must last \geq 8 weeks).
- Hemoglobin greater than 11 g/dL.
- Neutrophils 1500/mm³ or more (not on a myeloid growth factor).
- Platelets 100 000/mm³ or more (not on a thrombopoietic agent).
- Blasts \leq 5%.
- No dysplasia. The presence of mild megaloblastoid changes may be permitted if they are thought to be consistent with treatment effect. However, persistence of pretreatment abnormalities (e.g., pseudo-Pelger Huet cells, ringed sideroblasts, dysplastic megakaryocytes) is not consistent with CR.

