6.5.1 ACCEPTABLE CONCOMITANT MEDICATIONS

All treatments that the investigator considers necessary for a subject's welfare may be administered at the discretion of the investigator in keeping with the community standards of medical care. All concomitant medication will be recorded on the case report form (CRF) including all prescription, over-the-counter (OTC), herbal supplements, and IV medications and fluids. If changes occur during the trial period, documentation of drug dosage, frequency, route, and date may also be included on the CRF. Subject may remain on anti-coagulation therapy as long as the PT or PTT is within therapeutic range of the intended use of anticoagulants

All concomitant medications received within 28 days before the first dose of trial treatment and 30 days after the last dose of trial treatment should be recorded. Concomitant medications administered after 30 days after the last dose of trial treatment should be recorded for SAEs and ECIs as defined in Section 8.2.

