12.5.5 RELAPSE (FOLLOWING A CR OR PR)

One or more of the following:

- Return to pretreatment bone marrow blast percentage.
- Decrement of > 50% from maximum remission response levels in neutrophils or platelets
- RBC transfusion dependence (≥ 2 units RBC transfusions over an 8 week period) or a reduction in hemoglobin concentration by ≥ 2 g/dL in the absence of acute infection, gastrointestinal bleeding, hemolysis, treatment hiatus etc.

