12.6 IDENTIFICATION AND FOLLOW-UP OF LESIONS IN AML

12.6.1 COMPLETE REMISSION (CR)

For subjects to be classified as being in CR, they must have bone marrow regenerating normal hematopoietic cells and achieve a morphologic leukemia-free state ($< 5\%$ bone marrow blasts in bone marrow, no blasts with Auer rods and no persistence of extramedullary disease) and must have an ANC $\geq 1 \times 10^9/\text{L}$ and platelet count $> 100 \times 10^9/\text{L}$

and they will be RBC and platelet transfusion independent (defined as 4 weeks without RBC transfusions and 1 week without platelet transfusion).

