12.6.5 RELAPSE

Relapse after CR, CRp, or CRi is defined as a reappearance of leukemic blasts in the peripheral blood or $\geq 5\%$ blasts in the bone marrow aspirate or biopsy not attributable to any other cause or reappearance or new appearance of extramedullary leukemia. Relapse after PR is similarly defined with reappearance of significant numbers of peripheral blasts and an increase in the percentage of blasts in the bone marrow aspirate to $>25\%$ not attributable to any other cause or reappearance or new appearance of extramedullary leukemia.

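### The MDS complete and partial remission criteria do not require hemoglobin above 11 g/dL to be reached without transfusion or an erythropoietic agent

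*Combined protocol and SAP*

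**What the plan says.** Protocol Section 12.5.1 defines MDS complete remission by a marrow condition and a list of peripheral-blood values that must last at least 8 weeks. In that list:

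- The neutrophil item reads "Neutrophils 1500/mm³ or more (not on a myeloid growth factor").
- The platelet item reads "Platelets 100 000/mm³ or more (not on a thrombopoietic agent").
- The hemoglobin item reads "Hemoglobin greater than 11 g/dL", with no condition on transfusion or on erythropoietic drugs.
- A blast ceiling of 5% also appears. It is a blood item: it precedes the dysplasia bullet, which the marrow paragraph points to with "see dysplasia qualifier under peripheral blood evaluation".

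Section 12.5.2 takes over the complete-remission criteria for partial remission, changing only the marrow item.

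Section 12.5.5 lists the events that count as relapse after either response, any one of which suffices. One is "RBC transfusion dependence", set at two or more units over 8 weeks.

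Elsewhere the appendix does address transfusion. For patients who were red-cell dependent at baseline, the major erythroid response in Section 12.5.8.3 needs transfusion independence for at least 8 weeks. For AML complete remission, Section 12.6.1 says "they will be RBC and platelet transfusion independent".

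On supportive care, Table 2 in Section 6.1.2 accepts a transfused hemoglobin at entry. Section 6.5.1 says "All treatments that the investigator considers necessary for a subject's welfare may be administered". The prohibited list in Section 6.5.2 names GM-CSF but neither transfusion nor erythropoietic agents.

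**The concern.** A hemoglobin value held up by transfusion reflects the support given at least as much as any recovery of the marrow. The MDS list recognizes this for neutrophils and, as regards drugs, for platelets, but not for hemoglobin. Because supported hemoglobin is permitted throughout the trial, the gap can be reached in practice.

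Two things are at stake. First, a supported patient could be counted in the overall response rate, which Sections 5.4 and 9.1.2 call the primary efficacy endpoint and Section 9.2.4.2.1 reports separately for MDS. Section 2.1 adds that a later expansion may favor disease subtypes with observed responses, so a single MDS responder could carry some weight. Second, the response rule and the relapse rule disagree about the same patient: transfusion does not prevent a response from being declared, but it ends one once declared.

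**Working it through.** The plan gives no figure to reproduce, since this is a question of definitions. The check applies the Section 12.5.1 list and the Section 12.5.5 items literally to four hypothetical MDS patients.

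**Common values (assumed for illustration).** Marrow blasts 3% (8% before treatment), normal maturation, no dysplasia, hemoglobin 11.5 g/dL, neutrophils 1,800/mm³, platelets 120,000/mm³, all held for 8 weeks.

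| Patient | Meets 12.5.1 list | Meets a 12.5.5 item |
|---|---|---|
| (a) No support | Yes | No |
| (b) 2 red-cell units in 8 weeks | Yes | Yes (transfusion item) |
| (c) On an erythropoietic agent | Yes | No |
| (d) 5% circulating blasts | Yes | No |

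Only patient (b) meets both rules.

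**Order of events.** Section 12.5.5 applies after a complete or partial remission, so units given during the qualifying 8 weeks come before the response. If transfusion continues at the same rate and the relapse window looks back 8 weeks, the item is met as soon as the response is declared. If only later units count, it is met within the next 8 weeks. The text does not say which.

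**Partial remission.** Section 12.5.2 sets aside marrow cellularity and morphology but keeps the hemoglobin item. The demanding marrow conditions that make patient (b) rare in complete remission therefore restrain partial remission less, and both count equally in the response rate.

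**Platelets.** The platelet item excludes thrombopoietic drugs but not platelet transfusion, so the same kind of gap exists. There is no matching relapse conflict, because Section 12.5.5 has no platelet-transfusion item.

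**Size.** One reclassified patient moves the pooled response rate by:

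- 1/26 = 0.038, or 3.8 points, at full enrollment;
- 1/12 = 0.083, or 8.3 points, if the trial stops at 12.

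Table 12 names an exact binomial test and Section 9.2.4.2.1 a reference rate of 10%. With n = 26 and a true rate of 10%, P(X ≥ 5) = 0.112 and P(X ≥ 6) = 0.040. At a one-sided 0.05 level (an assumption, as none is stated), one patient changes the result only when the count lies at the boundary of 5 versus 6 responders. The number of MDS patients is not given, so the effect on the MDS-specific rate cannot be sized.

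**The case against.** Several stronger readings are tempting, and the documents do not support them.

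- *The patient is in remission and relapse on the same dates.* Section 12.5.5 concerns relapse following a response. The conflict comes directly after the response is declared, not during the qualifying weeks.
- *Erythropoietic agents or circulating blasts also produce the conflict.* Neither is an item in Section 12.5.5. The rule on "reappearance of leukemic blasts in the peripheral blood" belongs to AML (Section 12.6.5). Different diseases may have different criteria, and no MDS section requires blood to be free of blasts.
- *Duration of response would be close to zero.* That follows from Section 3.2, which ends duration at progression or relapse. Section 5.4 ends it at progression, which for MDS (Section 12.5.6) is defined by blasts alone. Section 12.5.8.7 uses progression, or progression or relapse after hematologic improvement. The consequence for duration is therefore unsettled.

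Three further objections carry weight. Sections 8.1.2.6.1 and 9.2.2.2 point to published MDS criteria, whereas Section 12.5 says that a modified set will be used. The published source cannot be consulted here, so the point is confined to the appendix text. The AML comparison is also limited: Section 12.6.3 expressly waives transfusion independence for CRi, and CRi counts as a response. It shows that the AML section states its position either way, whereas the MDS list is silent on hemoglobin. Finally, the enrollment, interim and go/no-go rules all rest on dose-limiting toxicity, and the response analysis is acknowledged to be small. This limits the severity but leaves the gap in place.

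**Conclusion.** The gap is real but minor. As written, Sections 12.5.1 and 12.5.2 count a patient with supported hemoglobin as an MDS responder. If the support is red-cell transfusion at two or more units per 8 weeks and it continues, Section 12.5.5 then calls the same patient relapsed.

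The conclusion assumes that assessors apply the appendix list literally. The case should be uncommon, because the neutrophil, platelet, dysplasia and 8-week conditions must also be met. No estimate of its frequency can be drawn from the documents. The primary endpoint and the 12/26 design are unaffected.

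Whether the 5% blood-blast line is an error or a deliberate threshold cannot be decided from the documents. It is a question for the sponsor.

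**What to change.** 1. In Section 12.5.1, word the hemoglobin item as: hemoglobin greater than 11 g/dL (untransfused and not on an erythropoietic agent). The 8-week requirement already in that section supplies the window.
2. Add untransfused to the platelet item, beside the existing drug condition. Partial remission then inherits both changes through Section 12.5.2, and complete remission, partial remission and the Section 12.5.5 relapse rule agree.
3. Record red-cell and platelet transfusions with dates and units for MDS patients. Sections 12.5.5 and 12.5.8 already need this information, but the concomitant-medication list in Section 6.5.1 does not name blood products.
4. Ask the sponsor to confirm whether the peripheral-blood blast ceiling of 5% in Section 12.5.1 is intended. No replacement value is proposed.

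The cost is an appendix edit and, if not already present, a transfusion field on the case report form. The MDS response rate may come out slightly lower. Sample size and the toxicity rules do not change. The edit should be in place before MDS responses are assessed.

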12.5.2 PARTIAL REMISSION (PR)

- All of the CR criteria (if abnormal prior to treatment), except:
- Bone marrow evaluation: Blasts decreased by 50% over pretreatment, or a less advanced MDS WHO classification than pretreatment. Cellularity and morphology are not relevant.

12.5.3 STABLE DISEASE

Failure to achieve at least a PR, but with no evidence of progression for \geq 2 months.

12.5.4 FAILURE

Death during treatment or disease progression characterized by worsening of cytopenias, with increase in the percent of bone marrow blasts (as defined in Section 6 below), and/or progression to an MDS FAB subtype more advanced than pretreatment.

12.5.5 RELAPSE (FOLLOWING A CR OR PR)

One or more of the following:

- Return to pretreatment bone marrow blast percentage.
- Decrement of > 50% from maximum remission response levels in neutrophils or platelets
- RBC transfusion dependence (≥ 2 units RBC transfusions over an 8 week period) or a reduction in hemoglobin concentration by ≥ 2 g/dL in the absence of acute infection, gastrointestinal bleeding, hemolysis, treatment hiatus etc.

12.5.6 DISEASE PROGRESSION

- A 50 % increase in blasts, depending on baseline blast percent.
- For patients with < 5% blasts: increase to $\geq 10\%$ blasts.
- For patients with 5% to 10% blasts: $\geq 50\%$ increase to > 10% blasts.
- For patients with 10% to 20% blasts: $\geq 50\%$ increase to $\geq 20\%$ blasts.

12.5.7 DISEASE TRANSFORMATION

- Transformation to AML ($\geq 20\%$ blasts).

12.5.8 CYTOGENETIC RESPONSE

Requires 20 analyzable metaphases when using conventional techniques. Analysis of data will require 20 metaphases before and after treatment, which must be done on bone marrow only (peripheral blood is not a substitute). Fluorescent *in situ* hybridization (FISH) may be used as a supplement to follow a specifically defined cytogenetic abnormality, but it is not a substitute for conventional cytogenetic studies. Cytogenetic response is defined as follows:

12.5.8.1 COMPLETE CYTOGENETIC RESPONSE:

Restoration of a normal karyotype in patients with a documented pre-existing clonal (>2 metaphases abnormal) chromosome abnormalities.

12.5.8.2 PARTIAL RESPONSE:

- 50% reduction in the percentage of Hematologic Improvement.
- Improvements must last ≥ 8 consecutive weeks.

12.5.8.3 ERYTHROID RESPONSE

Major Erythroid Response: Transfusion-independence for ≥ 8 consecutive weeks for patients

who were RBC transfusion-dependent at baseline AND a ≥ 1 g/dL hemoglobin rise compared to mean pre-transfusion baseline value; or a > 2 g/dL rise in hemoglobin without transfusion for non-transfusion dependent patients.

Minor Erythroid Response: The mean hemoglobin is sustained 1.0 to 2.0 g/dL above the baseline value for a minimum of 8 weeks; or a 50% or greater decrease in 8-week RBC transfusion requirements compared to baseline.

12.5.8.4 PLATELET RESPONSE

Major Platelet Response: For patients with a pretreatment count $< 100,000/\text{mm}^3$, an absolute increase of $\geq 30,000/\text{mm}^3$; for platelet transfusion-dependent patients, stabilization of platelet counts and platelet transfusion independence.

Minor Platelet Response: For patients with a pretreatment platelet count $< 100,000/\text{mm}^3$, a $> 50\%$ increase in platelet count with a net increase $> 10,000/\text{mm}^3$ but $< 30,000/\text{mm}^3$.

12.5.8.5 NEUTROPHIL RESPONSE

Major Neutrophil Response: For pretreatment ANC $< 1500/\text{mm}^3$, $\geq 100\%$ increase, or an absolute increase of $\geq 500/\text{mm}^3$, whichever is greater.

Minor Neutrophil Response: For ANC $> 1500/\text{mm}^3$ before therapy, ANC increase of at least 100%, but absolute increase less than $500/\text{mm}^3$, lasting greater than 8 weeks (56 days).

12.5.8.6 PROGRESSION/RELAPSE FOLLOWING ERYTHROID HEMATOLOGIC IMPROVEMENT

For patients who achieve RBC transfusion independence: requirement for ≥ 2 units RBC transfusion in an 8 week period or a reduction in hemoglobin concentration by ≥ 2 g/dL in the absence of acute infection, gastrointestinal bleeding, hemolysis, etc., reaching a hemoglobin < 9.5 g/dL.

For patients who achieve $\geq 50\%$ decrease in RBC transfusions: return to pre-treatment RBC transfusion requirement over an 8 week period.

12.5.8.7 DURATION OF RESPONSE

Time to disease progression (as per Bone Marrow Responses above) or progression/relapse following hematologic improvement (as per Hematologic Improvement above).

12.6 IDENTIFICATION AND FOLLOW-UP OF LESIONS IN AML

12.6.1 COMPLETE REMISSION (CR)

For subjects to be classified as being in CR, they must have bone marrow regenerating normal hematopoietic cells and achieve a morphologic leukemia-free state ($< 5\%$ bone marrow blasts in bone marrow, no blasts with Auer rods and no persistence of extramedullary disease) and must have an ANC $\geq 1 \times 10^9/\text{L}$ and platelet count $> 100 \times 10^9/\text{L}$

and they will be RBC and platelet transfusion independent (defined as 4 weeks without RBC transfusions and 1 week without platelet transfusion).

12.6.2 COMPLETE REMISSION WITH INCOMPLETE PLATELET RECOVERY (CRP)

For subjects to be classified as being in CRp, they must achieve CR except for incomplete platelet recovery ($<100 \times 10^9/L$).

12.6.3 COMPLETE REMISSION WITH INCOMPLETE HEMATOLOGICAL RECOVERY (CRI)

For subjects to be classified as being in CRi, they must fulfill all the criteria for CR except for incomplete hematological recovery with residual neutropenia $<1 \times 10^9/L$ and/or platelet count $>100 \times 10^9/L$. RBC and platelet transfusion independence is not required.

12.6.4 PARTIAL REMISSION (PR)

For subjects to be classified as being in PR, they must meet the criteria for CRi but only require a decrease of at least 50% in the percentage of blasts in the bone marrow with the total marrow blasts between 5% and 25% inclusive.

12.6.5 RELAPSE

Relapse after CR, CRp, or CRi is defined as a reappearance of leukemic blasts in the peripheral blood or $\geq 5\%$ blasts in the bone marrow aspirate or biopsy not attributable to any other cause or reappearance or new appearance of extramedullary leukemia. Relapse after PR is similarly defined with reappearance of significant numbers of peripheral blasts and an increase in the percentage of blasts in the bone marrow aspirate to $>25\%$ not attributable to any other cause or reappearance or new appearance of extramedullary leukemia.

12.6.6 DEFINITIVE PROGRESSION

NHL, HL, MDS, and AML response and progression data will be subjected to IRC review. The subject should continue on study pending confirmation of progression by the IRC.

12.6.7 ACUTE GVHD GRADING ⁴²

The Gluckenberg scale will be used to grade and stage acute GVHD.

Organ	Stage	Description
Skin	1	Maculopapular rash over <25 percent of body area
	2	Maculopapular rash over 25 to 50 percent of body area
	3	Generalized erythroderma
	4	Generalized erythroderma with bullous formation and often with desquamation
Liver	1	Bilirubin 2.0 to 3.0 mg/dL; SGOT 150 to 750 international units
	2	Bilirubin 3.1 to 6.0 mg/dL
	3	Bilirubin 6.1 to 15.0 mg/dL
	4	Bilirubin >15.0 mg/dL
Gut	1	Diarrhea >30 mL/kg or >500 mL/day
	2	Diarrhea >60 mL/kg or >1000 mL/day
	3	Diarrhea >90 mL/kg or >1500 mL/day
	4	Diarrhea >90 mL/kg or >2000 mL/day; or severe abdominal pain with or without ileus
Glucksberg grade		
I – Stage 1 or 2 skin involvement; no liver or gut involvement; ECOG PS 0		
II – Stage 1 to 3 skin involvement; Grade 1 liver or gut involvement; ECOG PS 1		
III – Stage 2 or 3 skin, liver, or gut involvement; ECOG PS 2		
IV – Stage 1 to 4 skin involvement; Stage 2 to 4 liver or gut involvement; ECOG PS 3		
International Bone Marrow Transplant Registry Severity Index		
A – Stage 1 skin involvement; no liver or gut involvement		
B – Stage 2 skin involvement; Stage 1 to 2 gut or liver involvement		
C – Stage 3 skin, liver, or gut involvement		
D – Stage 4 skin, liver, or gut involvement		

